#### Please note:

- IOP readings should not be adjusted for corneal thickness.
- The tonometer should be calibrated prior to or at the Baseline Visit (Visit 1) and calibration should be documented.

### 4. Blood Pressure

Resting state blood pressure will be measured after the subject has been seated quietly for at least 5 minutes. Blood pressure will be measured with a sphygmomanometer with appropriate size cuff and a stethoscope or with a measurement device.

### 5. Pregnancy Testing

A urine human chorionic gonadotropin (hCG) pregnancy test (only for females who are not diagnosed as postmenopausal or surgically sterile) will be used in this study and performed at the Baseline Visit to immediately confirm non-pregnancy eligibility for women of childbearing potential.

### 6. [REDACTED] Questionnaire

The investigator (or designee) will administer the [REDACTED] Questionnaire and record the subject's responses on the appropriate CRF at Visit 3 (Week 12).

**7. [REDACTED] Questionnaire**

The investigator will complete the [REDACTED] Questionnaire at Visit 3 (Week 12) for all subjects who complete the study.

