### **8.3.2 [REDACTED] Questionnaire**

At Visit 3 (Week 12), the investigator will complete a [REDACTED] Questionnaire (see [Appendix 2](#) for detailed information on this questionnaire).

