### **9.1 Completion of the Study**

Each subject who completes the entire Schedule of Visits as specified in this protocol will have completed the study.

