### **9.2 Subject Discontinuation**

A subject may be withdrawn from the study prior to completion for any reason and categorized as follows:

- AEs
- Lost to follow-up
- Other (administrative reasons, etc.)

If a subject discontinues from the study for any reason at any point beyond his/her Baseline Visit (Visit 1), he/she should be requested to return for a final visit at which time all Visit 3 (Week 12) procedures should be performed according to the protocol Schedule of Visits/Procedures (see [Appendix 4](#)).

Subjects who are prematurely withdrawn or discontinued from the study will not be replaced.

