#### 2) Investigator Questionnaire

At Week 12 (Visit 3) only. A [REDACTED] investigator-administrated questionnaire (see protocol Appendix 2) as the end-of-study assessment of treatment. [REDACTED]  
[REDACTED]

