## 4 STUDY PARAMETERS

### 4.1 Subject Disposition

Subjects who completed the Week 12 (Visit 3) visit will be considered as having reached Study Completion, otherwise, they will be classified in the Study Discontinuation group.

Reason(s) for study discontinuation will be recorded and could include the following:

- Adverse event
- Lost to follow-up
- Other

Time in the study will be computed as following:

$$\text{Time in Study (Study Duration)} = \text{Last Date in study} - \text{Date of First Dose} + 1$$

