### 6.2.3 Treatment Discontinuation and Rescue Medications

No rescue medication is proposed in this study. The subject will be exited from the study after discontinuation from the study treatment.

Efficacy assessment collected from the treatment discontinuation exit will be mapped to the next scheduled visit and considered as observed data. (i.e., the mapping will be performed prior to any data imputation if any).

Safety assessment for the treatment discontinuation exit will not be mapped. Instead, it will be treated as the last assessment during treatment period.

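### Appendix 5 ties the investigator questionnaire to subjects who complete the study, while Section 9.2 asks for every Visit 3 procedure at early exit; the two need reconciling

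*Protocol*

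**What the plan says.** The passages that bear on the investigator questionnaire are these.

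- **Protocol Appendix 5, item 7:** the investigator fills in the form "at Visit 3 (Week 12) for all subjects who complete the study".
- **Protocol 9.2:** for a subject who discontinues after baseline, whatever the reason, "he/she should be requested to return for a final visit at which time all Visit 3 (Week 12) procedures should be performed".
- **Protocol 7.6 and Appendix 4:** both list the form at Visit 3. Appendix 4 marks it as required, and its footnote 7 says only who fills it in.
- **Protocol 8.3.2:** the section begins "At Visit 3 (Week 12), the investigator will complete a" and goes on to name the questionnaire. It sets no limit to completers.
- **Protocol 9.1:** "Each subject who completes the entire Schedule of Visits as specified in this protocol will have completed the study".
- **SAP 4.1:** "Subjects who completed the Week 12 (Visit 3) visit will be considered as having reached Study Completion"; everyone else is classed as discontinued.
- **SAP 6.2.3:** "The subject will be exited from the study after discontinuation from the study treatment".
- **SAP 3.1.3, item 2:** under exploratory and other assessments, the form is timed "At Week 12 (Visit 3) only" and described as a "questionnaire (see protocol Appendix 2) as the end-of-study assessment of treatment".

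**The concern.** The SAP treats this form as a judgement of the treatment at the end of the study. Adverse events are a listed reason for discontinuation in both documents. A judgement of treatment collected only from subjects who stayed to Week 12 therefore describes a group selected partly by how the treatment went. The study has a single arm, so no control group is subject to the same selection.

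There is also a practical risk. About 32 centers will read the same protocol. Some may work from Appendix 5 and leave the form blank at early exit; others may work from Section 9.2 and complete it. The result would then mix completers with an uncontrolled share of discontinuers, and its denominator would depend on site habit.

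**Working it through.** The documents give no figure to reproduce. SAP 3.3 says that no sample size calculation was done, and no dropout rate appears. The main check is a comparison of texts.

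**Step 1. Is an early-exit subject a completer?** Under Protocol 9.1 the subject needs the whole visit schedule, and under SAP 4.1 the Week 12 visit. SAP 6.2.3 takes a subject who stops treatment out of the study. A subject who leaves before Week 12 is thus a discontinuation.

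**Step 2. What does each rule give?**

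| Subject | Appendix 5, item 7 | Section 9.2 with 7.6 and Appendix 4 |
|---|---|---|
| Completes Week 12 | Form | Form |
| Exits early, returns for final visit | No form provided for | Form |
| Exits early, does not return | No form provided for | No visit at which to complete it |

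The rules differ in the middle row only.

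**Step 3. Does other visible text settle it?** No.

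- SAP 1.1 records no changes from the protocol.
- SAP 6.2.3 says how efficacy and safety data from a treatment-discontinuation exit are handled, but no rule for questionnaires is visible.
- Protocol 9.0 names completed and discontinued subjects together when it means both, so the wording of item 7 cannot safely be read as shorthand for everyone.
- Appendix 5, item 6 (the other questionnaire) has no completer wording.

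**Step 4. How many subjects could be affected?** Let N = 250 (planned enrollment) and d = the share discontinuing (assumed). The number with no form under Appendix 5 is N × d:

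- d = 5%: 250 × 0.05 = 12.5
- d = 10%: 250 × 0.10 = 25
- d = 20%: 250 × 0.20 = 50
- d = 30%: 250 × 0.30 = 75

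These are upper limits on what Section 9.2 could recover, because not every discontinuing subject will return.

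**Step 5. What could that do to a reported percentage?** Suppose, purely for illustration, that the form yields a favourable/unfavourable rating. Let p be the favourable share in completers and q the share in those who stop. The all-subject share is (1 − d)p + dq, so the completers-only figure differs from it by d(p − q). With p = 80% assumed:

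| d | Gap if q = 50% | Gap if q = 20% | All-subject share for q from 0% to 100% |
|---|---|---|---|
| 5% | 1.5 points | 3 points | 76% to 81% |
| 10% | 3 points | 6 points | 72% to 82% |
| 20% | 6 points | 12 points | 64% to 84% |
| 30% | 9 points | 18 points | 56% to 86% |

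If q = p the gap is zero. The last column lies on both sides of 80%, so the sign of the gap depends on q, about which the documents give no information.

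**The case against.** The strongest reply is that the protocol as a whole does not restrict the form. One sentence in an appendix mentions completers, and it does not say that only they are to be assessed. Section 9.2 is the passage written for discontinuing subjects, and a site that follows it will complete the form at early exit. **This stands in part.** Exclusion is certain only if Appendix 5 governs. But nothing says which passage governs, and that is the defect.

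Four stronger readings are tempting, and the documents do not support them.

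- *The SAP also imposes a completers-only rule.* Its timing phrase reads as a label for the scheduled timepoint; SAP 3.1.2 uses similar shorthand for other assessments. SAP Section 6 also calls Visit 3 the end-of-treatment visit and gives it a window from Day 64 to the end of the study.
- *Both questionnaires are affected.* Only item 7 carries the completer wording.
- *Section 9.2 guarantees a form from every discontinuing subject.* It asks for a return visit, and loss to follow-up is a listed reason for leaving.
- *The reported result will be too favourable by a known amount.* The items are redacted and their analysis is not visible, so it is unknown whether any item is a favourable/unfavourable rating or what denominator is planned. A favourable tilt is plausible when subjects who stop for adverse events are missing, but it cannot be derived.

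**Conclusion.** The conflict is real and can be checked from legible text. For a subject who exits early and returns, Appendix 5 provides for no investigator questionnaire and Section 9.2 asks for one. The consequence is either omission of early stoppers or uneven collection across sites, according to which passage is followed.

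The only scale available is the 12 to 75 subjects in Step 4, which rests wholly on the assumed 5% to 30% discontinuation. The percentage gaps in Step 5 show sensitivity and are not estimates. The assessment is exploratory and the study descriptive, so no conclusion about IOP changes. A reader might infer a deliberate choice to assess completers only; the unrestricted wording elsewhere in the protocol points at least as much to a drafting inconsistency. The point should still be corrected, since a form not completed at exit may be hard to recover later.

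**What to change.** 1. Amend Protocol Appendix 5, item 7 so that the investigator questionnaire is completed for all subjects, at Visit 3 or at the early-exit visit.
2. Align the timing in SAP 3.1.3, item 2 to Visit 3 or early exit.
3. Report the number of completers and the number of discontinuers with a form, so that the denominator is visible.

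Appendix 5, item 6 needs no correction.

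The cost is a few changed lines and a few more forms. No visit is added, because Section 9.2 already requests one. The exploratory figure may turn out less favourable than one from completers alone. Some discontinuing subjects will still lack a form, which the counts in point 3 will show.

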**8. Adverse Events**

At both Visit 2 (Week 6) and Visit 3 (Week 12), the investigator (or designee) will question each subject regarding adverse experiences that may have occurred since a previous visit. Subjects will be queried "How are you feeling?" and all AEs will be recorded in the CRFs, including severity, action taken, and relationship to study medication.

## 1 INTRODUCTION

The purpose of this statistical analysis plan (SAP) – Module I is to describe the related procedures and statistical methodologies used to process the study data, analyze the study data, and report the results for Protocol MA-RHO-18-002 sponsored by Aerie Pharmaceuticals, Inc (Sponsor).

This SAP should be read in conjunction with the latest version of the designated study protocol, its case report forms (CRF), and the related SAP Module II – Tables, Graphs, Figures, and Listing.

### 1.1 Changes from Protocol

Not applicable.

## 2 STUDY OBJECTIVES

The study objective is to evaluate the intraocular pressure (IOP) lowering efficacy of netarsudil 0.02% when used as monotherapy or when used concomitantly with other IOP-lowering agents in subjects with elevated IOP due to open-angle glaucoma or ocular hypertension in a real-world setting.

## 3 STUDY DESIGN

This is a phase 4, prospective, multi-center, open-label, single arm study. Approximately **250** study subjects in about **32** study sites in the U.S. will be enrolled. **Both** eyes of each subject will be treated and evaluated, but only one eye will be included in the efficacy analysis (see study protocol Section 11.3.2.1).

Study subjects must be diagnosed with open-angle glaucoma or ocular hypertension and meet the study Inclusion/Exclusion Criteria (see study protocol Sections 4.3.1 and 4.3.2).

### 3.1 Study Measurements

#### 3.1.1 Primary Efficacy Measure

The primary efficacy measurement is **IOP** (mmHg) measured using a Goldmann applanation tonometer affixed to a slit lamp.

### **3.1.2 Safety Assessments**

- 1) Adverse Events**
- 2) Best-corrected Visual Acuity (BCVA)**

BCVA will be measured for both eyes by the investigator (or designee) at the Baseline Visit (Visit 1) and at both Visit 2 (Week 6) and Visit 3 (Week 12) using a Snellen Visual Acuity Chart (see protocol Appendix 5 for detailed information on this examination).

- 3) Biomicroscopy**

Biomicroscopy will be performed by the investigator (or designee) for both eyes at all visits by slit lamp examination without pupil dilation for the following locations:

- **Lids/Lashes (upper and lower)** – erythema, edema
- **Conjunctiva (Palpebral and Bulbar)** – Hyperemia, Edema, Follicles
- **Cornea** – Edema, Staining/Erosion
- **Anterior Chamber** – Cells, Flare
- **Lens Status** - Aphakic, Phakic, Pseudophakic, Not done. And if phakic, **Lens Appearance**

Observations for the slit lamp Biomicroscopy examination (except lens status) will be graded on a 5-point scale as follows (see protocol appendix 5 - Examination Procedures for detailed grading definition for each assessment):

- 0 = None
- 0.5 = Trace
- 1 = Mild
- 2 = Moderate
- 3 = Severe

- 4) Pregnancy Testing**

A urine human chorionic gonadotropin (hCG) pregnancy test (negative, positive). Only at Baseline Visit for females who are not diagnosed as postmenopausal or surgically sterile.

- 5) Blood Pressure (mmHg)**

At all visits. Systolic and Diastolic

- 6) Central Corneal Thickness (µm)**

Baseline only.

### 3.1.3 Exploratory/Other Assessments

#### 1) Patient Questionnaire

At Week 12 (Visit 3) only. A [REDACTED] investigator-administrated patient questionnaire (see protocol Appendix 1) as the end-of-study assessment of treatment. [REDACTED]  
[REDACTED]

#### 2) Investigator Questionnaire

At Week 12 (Visit 3) only. A [REDACTED] investigator-administrated questionnaire (see protocol Appendix 2) as the end-of-study assessment of treatment. [REDACTED]  
[REDACTED]

### 3.2 Study Visits and Schedule of Events

Subjects will participate in the study for approximately 12 weeks. There will be a total of 3 clinic visits: Screening/Baseline (Day 0), 2 in-treatment visits at Week 6 ( $\pm 7$  days) and Week 12 ( $\pm 7$  days). Activities and medical procedures to be performed at each study visit are summarized in the study protocol Appendix 4.

### 3.3 Sample Size Considerations

Approximately 250 subjects will be enrolled at about 32 sites. No sample size calculation was performed.

### 3.4 Randomization and Masking

Not applicable.

### 3.5 Study Drug Administration and Compliance

Subjects will receive [REDACTED] netarsudil 0.02% at the Baseline Visit (Visit 1) and at the Week 6 (Visit 2). They will self-administer the eye drop in **each** eye in the evening. (See protocol Section 5.1.4 and 5.1.5 for details).

No washout period required for subjects replacing prior IOP-lowering therapy.

### 3.6 Concomitant Therapy

If netarsudil 0.02% is to be used concomitantly with other topical ophthalmic drug products to lower IOP, each drug product should be administered at least 5 minutes apart to prevent washout.

Therapy considered necessary for a subject's welfare will be given at the discretion of the investigator and documented during the course of the study. The use of any concurrent medication (prescription or over-the-counter, including herbal medications) is to be recorded in a subject's source documentation (charts), as well as in the case report forms (CRFs), noting the date, dosage, frequency, start date, and reason for taking the medication(s).

### 3.7 Adverse Events (AE)

An AE is defined as any untoward medical occurrence in a subject during the course of a study. An AE can, therefore, be any unfavorable and unintended sign (including a clinically significant abnormal laboratory finding), symptom, or disease temporally associated with the use of an investigational or marketed medicinal product, whether or not considered related to the investigational or marketed medicinal product. AEs include any illness, sign, symptom, or clinically significant laboratory test abnormality that has appeared or worsened during the course of the clinical trial, regardless of causal relationship to the study medication(s) under study.

AEs may be either spontaneously reported or elicited during questioning and examination of a subject.

The following information will be collected and tabulated for all AEs:

- AE description
- AE location (OD, OS, OU, Non-ocular)
- Start date
- Whether the AE is ongoing (Yes, No)
- End date
- Severity (Mild, Moderate, Severe. See protocol section 10.1.1 for severity definition)
- Whether the AE is serious (Yes, No)
- Whether the AE is congenital anomaly or birth defect (Yes, No)
- Whether the AE led to death (Yes, No)
- Whether the AE led to disability or permanent damage (Yes, No)
- Whether the AE led to hospitalization (Yes, No)
- Whether the AE is life threatening (Yes, No)
- Whether the AE led to other important medical event (Yes, No)
- Relationship to study treatment (Not related, Unlikely related, Possibly related, Related)
- Action taken with study treatment (Not changed, Drug interrupted, Drug withdrawn, N/A)
- Whether a concomitant or additional treatment given (Yes, No)

- Whether the AE led to study discontinuation (Yes, No)
- Whether any other action(s) taken (Yes, No. If yes, specification for other actions)
- Outcome (Fatal, Not Recovered/Not resolved, Recovered/Resolved, Recovered/Resolved with sequelae, Recovering/Resolving, Unknown)

The AEs and SAEs will be collected from visits 2 and 3 as well as upon subject report after visit 1 and will continue until the final protocol required visit and/or continue through resolution, or stabilization or the investigator assesses them as chronic or stable or the subject's participation in the trial ends, whichever occurs first.

## 4 STUDY PARAMETERS

### 4.1 Subject Disposition

Subjects who completed the Week 12 (Visit 3) visit will be considered as having reached Study Completion, otherwise, they will be classified in the Study Discontinuation group.

Reason(s) for study discontinuation will be recorded and could include the following:

- Adverse event
- Lost to follow-up
- Other

Time in the study will be computed as following:

$$\text{Time in Study (Study Duration)} = \text{Last Date in study} - \text{Date of First Dose} + 1$$

### 4.2 Study Treatment Group

[figure not shown]
All subjects will receive netarsudil 0.02% either as first-line monotherapy, as a replacement of prior IOP-lowering medication or used concomitantly with other IOP-lowering medications as determined by the treating physician.

### 4.3 Primary Efficacy Endpoints

The primary efficacy measure is the intraocular pressure (IOP, mmHg). The primary efficacy endpoint is the percent (%) IOP reduction from baseline.

The primary efficacy analysis will be performed for mITT and PP populations. There will be no imputation for missing Week 12 assessment.

#### 4.4 Exploratory/Other Assessments

#### 4.5 Safety Endpoints

The Medical Dictionary for Regulatory Activities nomenclature (MedDRA V22.0 at time of SAP publication, or the current version when superseded) will be used to code AEs.

Treatment-emergent AEs are any AEs with an onset date equal to or after the date of the first dose of the study eye drop. A pre-existing event that worsens after the first dose date is considered a treatment emergent event. Treatment-related AEs are any AEs with a relationship of unlikely related, possibly related or related to study treatment, or AEs with a missing relationship.

Safety endpoints include:

- Adverse events
- Best-corrected visual acuity
- Biomicroscopy
- Blood pressure

All treatment-emergent AEs/SAEs will be summarized with frequency distributions by treatment group, system organ class, and preferred term as well as by ocular versus non-ocular. Specific AEs/SAEs occurring with a frequency of 5% or more will be summarized in a separate listing.

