### 10.1.2 Relationship of Adverse Events

The relationship of the AE(s) to the study medication(s) must be specified by the investigator using the following definitions:

Not Related: The event is clearly related to other factors, such as subject's clinical condition, therapeutic interventions, concomitant disease, or therapy administered to the subject and does not follow a known response pattern to the product.

Unlikely Related: The event is most probably caused by other etiologies, such as participant's underlying condition, therapeutic intervention, or concomitant therapy; or the delay between administration and the onset of the AE is incompatible with a causal relationship. Therefore, there is not a reasonable possibility that the AE was caused by the study medication.

Possibly Related: The event follows a reasonable, temporal sequence from the time of study medication administration and/or follows a known response pattern to the study medication but could have been produced by other factors, such as the subject's clinical state, therapeutic interventions, or concomitant therapy administered to the subject.

Related: The event follows a reasonable, temporal sequence from the time of study medication administration and/or follows a known response pattern to the study medication and cannot be reasonably explained by other factors, such as subject's clinical state, therapeutic interventions, or concomitant therapy administered to the subject and either occurs immediately following study medication administration, improves on stopping the study medication, reappears on repeat exposure, or there is a positive reaction at the application site.

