##### **11.3.3.1 Adverse Events**

All treatment-emergent AEs/SAEs will be summarized with frequency distributions by treatment group, system organ class, and preferred term using version 21.1 of the Medical Dictionary for Regulatory Activities (MedDRA) as well as by ocular versus non-ocular. Specific AEs/SAEs occurring with a frequency of 5% or more will be summarized in a separate listing.

Descriptive statistics will also be provided as data summaries.

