### 6.6.1 Adverse Events

All AEs reported during the study period reported for **both** eyes will be recorded and coded using MedDRA terminology and analyzed. An AE will be considered as treatment-emergent adverse event (TEAE) if it has an onset during the treatment period. A pre-existing event that worsens after the first dose date is considered a treatment emergent event.

The incidence of all TEAEs will be summarized using system organ class and preferred term. Adverse events will also be presented by relationship and severity. Further, serious adverse events and those events leading to discontinuation will also be presented.

Separate analyses will be performed for ocular and non-ocular TEAEs. For ocular TEAEs, the analytical unit will be eyes, and the total number of eyes in the safety population will be the denominator for incident rate of a specific ocular TEAE. For non-ocular TEAEs, subject will be the analytical unit and the number of subjects in the safety population will be the denominator for a specific non-ocular TEAE.

A subject/eye may have more than one AE per system organ class and preferred term. At each level of subject/eye summarization, a subject/eye will be counted once if 1 or more events were recorded and the highest severity will be reported. In cases where severity or relationship is missing, the most conservative approach will be taken (i.e. highest severity and assumed to be related).

The following summary tables of AEs will be presented:

- Adverse Events
  - Overall summary

- Ocular AEs
- By preferred term
- By preferred term and severity
- By frequency for SAEs
- By frequency for most common non-serious AEs

Most common non-serious AEs are any preferred term AE that at least 5% of the subjects report at least once.

- Treatment-Related AEs
  - Overall summary
  - By preferred term
  - By preferred term and severity
  - By preferred term and treatment session
  - Duration of AEs

The following overall summary will be presented:

- Total number and percentage of AEs
  - All AEs
  - Mild AEs
  - Moderate AEs
  - Severe AEs

Percentages for the total number of mild, moderate, and severe AEs will be based on the total number of all AEs.

- Total number and percent of subjects with
  - At least one AE
  - At least one SAE
  - No severe AEs but at least one moderate AE
  - No severe/moderate AEs but at least one mild AE
  - At least one AE leading to discontinuation

- Total number and percent of subjects with

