  - All ocular-related AE
  - Mild ocular-related AE
  - Moderate ocular-related AE
  - Severe ocular-related AE
  - At least one ocular-related AE leading to discontinuation
  
- Total number of subjects who died (Treatment-emergent only)

Subject level listing will be provided with related information that include AE onset/resolution date, study days, duration, preferred terms, relationship to study treatment, action taken, outcome, and sorted by subject ID and onset date.

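### The SAP counts adverse events rated unlikely related as treatment-related, although the protocol gives that rating to events with no reasonable possibility of drug causation

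*SAP*

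**What the plan says.** SAP 3.7 collects causality on four levels: not related, unlikely related, possibly related and related. Protocol 10.1.2 uses the same four and tells investigators what each means.

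SAP 4.5 reduces the scale to a two-way split: "Treatment-related AEs are any AEs with a relationship of unlikely related, possibly related or related to study treatment, or AEs with a missing relationship".

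Protocol 10.1.2 gives two routes to an unlikely rating. Either another cause is the more probable explanation, or "the delay between administration and the onset of the AE is incompatible with a causal relationship". The definition then concludes: "Therefore, there is not a reasonable possibility that the AE was caused by the study medication".

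SAP 6.6.1 lists five displays for treatment-related events: an overall summary, by preferred term, by preferred term and severity, by preferred term and treatment session, and duration. On missing values the same section says: "In cases where severity or relationship is missing, the most conservative approach will be taken (i.e. highest severity and assumed to be related". SAP 1.1 lists no changes from the protocol.

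**The concern.** Investigators rate each event using the protocol's definitions. The SAP then places one of those ratings under a label that says the opposite of what the rating means. An event judged to have no reasonable possibility of drug causation, including one whose timing does not fit, would be tabulated as treatment-related.

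The label carries particular weight in this design. The study has a single arm (SAP 3), so no control rate helps to separate drug effects from background events. Subjects may take netarsudil alongside other IOP-lowering medication (Protocol 4.3.1, SAP 4.2), and Protocol 10.1.2 names concomitant therapy among the alternative causes behind an unlikely rating. An event that the investigator attributes to another drug can therefore appear in the treatment-related tables for this one.

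**Working it through.** The plan states no figure on this point, so there is nothing to reproduce. The check compares the texts and then works out what the rule does to the tables.

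**Step 1. The two texts, level by level**

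| Rating | Meaning in Protocol 10.1.2 (paraphrased) | Treatment-related under SAP 4.5? |
|---|---|---|
| Not related | clearly due to something else | No |
| Unlikely related | other cause more probable, or timing does not fit; no reasonable possibility of causation | **Yes** |
| Possibly related | plausible timing and/or known pattern, but other causes could explain it | Yes |
| Related | plausible timing and/or known pattern, not explained otherwise, with supporting evidence | Yes |
| Missing | not defined | Yes |

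The SAP class holds 3 of the 4 levels plus missing. A class that follows the protocol's meaning holds 2 of the 4 plus missing.

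**Step 2. Is a reason given elsewhere?** The conservative rule in SAP 6.6.1 applies when severity or relationship is missing. It accounts for the missing row of the table, not for a recorded unlikely rating. SAP 1.1 offers nothing. Protocol 10.1 does mention unlikely together with possibly related and related, but only to say for which events the outcome should especially be reported; it creates no analysis class.

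**Step 3. Effect on event counts.** Let R be the number of events rated possibly related, related or missing, and U the number rated unlikely. The SAP count is R + U, so the excess is exactly U. The documents do not give U.

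**Step 4. Effect on subject counts.** SAP 6.6.1 says "a subject/eye will be counted once if 1 or more events were recorded and the highest severity will be reported". The excess is therefore k, the number of subjects whose only events in the class are unlikely. Assuming a safety population equal to the planned 250 (Protocol 11.1, SAP 3.3), the rise in a subject-level rate is 100 × k / 250 percentage points:

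- k = 0: 0
- k = 1: 0.4
- k = 5: 2.0
- k = 10: 4.0

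The values of k are illustrative. Ocular events are counted per eye. With both eyes treated, the denominator is 2 × 250 = 500, so one such eye adds 100 / 500 = 0.2 points.

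**Step 5. Severity and duration.** These toy cases show direction only.

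- Severity: 10 subjects each have a mild, possibly related event, and 2 of them also have a severe, unlikely event. Under the highest-severity rule, at the any-event level, the total stays at 10, mild goes from 10 to 8 and severe from 0 to 2.
- Duration: events of 10, 20 and 30 days have a median of 20. Adding one unlikely event of 5 days gives (10 + 20) / 2 = 15. Adding one of 60 days gives (20 + 30) / 2 = 25.

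Totals in the class can only rise or stay the same. Individual severity cells and the duration summary can move either way.

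**Step 6. How many displays?** Of the five listed, the one by treatment session uses a term that neither document defines. At least four displays are affected, and the fifth as well if it is produced.

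**The case against.** The best defence is that no rule is broken. The protocol defines no pooled treatment-related class. Its own safety plan is limited to treatment-emergent frequencies ("All treatment-emergent AEs/SAEs will be summarized with frequency distributions by treatment group, system organ class, and preferred term"), and Protocol 11.3 allows the SAP to add analyses. SAP 4.5 is explicit and can be programmed. Where to cut a four-level scale is partly the analyst's choice, this cut cannot hide a related event, and Protocol 10.1 draws the same line for outcome reporting. Unlikely is also a less certain rating than not related. Finally, the SAP promises a breakdown: "Adverse events will also be presented by relationship and severity". The subject listing carries "preferred terms, relationship to study treatment, action taken, outcome" as well, so the narrower class can be rebuilt.

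Much of this stands. The conflict is with the meaning of a rating, not with a competing definition or a planned protocol analysis. The grouping is cautious for counts, and the listing does allow the narrower class to be rebuilt by hand.

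Three parts do not remove the problem. Both routes to an unlikely rating lead to the same protocol conclusion, so the conflict covers the whole category and not only events with incompatible timing. The outcome-reporting sentence in Protocol 10.1 concerns follow-up and does not say what counts as drug-related. And although SAP 6.6.1 promises presentation by relationship, its list of summary tables names no by-relationship table. Such a table, or a clarifying footnote, may exist in SAP Module II, which is not among the documents available here.

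**Conclusion.** The concern holds. Followed as written, SAP 4.5 produces treatment-related tables that contradict the investigators' own ratings as the protocol defines them, without a stated reason.

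The consequence is limited and its size unknown, with a minimum of zero. Treatment-related counts can be overstated but not understated. Overall treatment-emergent rates and all efficacy results are untouched. The conversion to percentage points rests on 250 treated subjects, with both eyes treated for the per-eye figure. How far readers would be misled also depends on whether Module II already labels these displays.

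**What to change.** In SAP 4.5, define treatment-related as possibly related, related, or relationship missing. This keeps the existing conservative handling of missing ratings and brings the label into line with Protocol 10.1.2. Add a by-relationship table to the list in SAP 6.6.1, so that the promised presentation has a named output and unlikely events stay visible.

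If the wider class is intended, say so in the SAP with the reason, and footnote every treatment-related display to state that it includes events rated unlikely related.

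The definition change is one line and needs no new data, since all four levels are already collected. The drawback is that treatment-related counts become somewhat less conservative. The change belongs before database lock, which is when Protocol 11.3 requires the SAP to be final.
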